1 PROTOCOL SYNOPSIS

Title: Efficacy and Safety of HemoStyp as an Adjunct for Management of Secondary Hemostasis in the Operative Setting

Protocol Number: UHP001

Investigational Device: HemoStyp

Sponsor: United Health Products, Inc.
[name]
[name]

Funding Organization: United Health Products, Inc.

Number of Sites: 10-15 sites

Number of Subjects: 236 subjects

Phase: Pivotal Study

Study Design: This study is a prospective, non-inferiority, multi-center, randomized, open-label trial to compare HemoStyp with Surgicel® in the management of bleeding during surgery.

Objectives: To assess efficacy and safety of HemoStyp as an adjunct for management of secondary hemostasis in the operative setting.

Subject Selection Criteria: Inclusion Criteria:
Subjects will be eligible to participate in this study if they meet all of the following criteria:

1. Elective procedure (non-laparoscopic thoracic, abdominal, or vascular surgery);
2. At time of surgery has mild to moderate soft tissue, vascular or parenchymal bleeding present at target bleeding site after primary standard conventional surgical hemostatic methods are proven to be ineffective or impractical;
3. Ages: Adult subjects ≥ 18 years of age; and
4. Subjects who are willing and able to sign consent.

Exclusion Criteria:
Subjects will not be eligible to participate in this study if they meet any of the following criteria:

1. Physical or psychological condition which would impair study participation;
2. Indications for emergency surgery;
3. Pre-operative laboratory findings of a hematologic disorder;
4. Subjects with history of moderate to severe allergies;
5. Subjects undergoing minimally invasive laparoscopic surgery;
6. Subjects who will require platelet or fresh frozen plasma transfusion during surgery;
7. Subjects who are pregnant or breast-feeding at the time of surgery; or
8. Subjects on P2Y12 platelet inhibitor (Plavix) less than 5 days prior to surgery, warfarin or Xa inhibitors not withheld per standard protocols for the management of anticoagulants pre-operatively.
9. Patients with a coagulation disorder, thrombocytopenia, liver disease and

anti-thrombin therapy.

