Statistical Analyses:	
Sample Size A non-inferiority comparison will be performed to determine if the hazard ratio with an overall sample size of 212 subjects (106 HemoStyp group and 106 Surgicel group) achieves 80% power at a 0.05 significance level when the hazard ratio is actually 1.33 (median survival is 3.0 minutes for HemoStyp and 4.0 minutes for Surgicel). The non-inferiority ratio is 0.75 (corresponding to margin of 1 minute). It is anticipated that the proportion of subjects observed with the event during the study is 0.90 for the HemoStyp group and 0.92 for the Surgicel group. These results assume that the hazard ratio is constant throughout the study and that Cox proportional hazards regression or the non-inferiority log-rank test is used to analyze the data.
 
It is anticipated that approximately 710 subjects will be screened to randomize approximately 234 subjects with an anticipated drop-out rate of approximately 10%.

Efficacy Analyses

Analysis of Primary Endpoint

The time to hemostasis will be measured from start of study treatment to the achievement of hemostasis at the target bleeding site (TBS), or to the end of the 10-minute observation period. The time to hemostasis will be considered as censored at the end of the 10-minute observation period. Time to hemostasis will be quantified in minutes according to its nominal time point. When re-bleeding occurs, and the cessation of bleeding is again achieved at a later time point, the effective time to hemostasis will be the latter time point. The time to hemostasis will be the time from start of study treatment to that last effective hemostatic time point.

The primary endpoint analyses will be based on Intent-to-Treat (ITT) population. The primary analysis is the test of non-inferiority of HemoStyp compared with Surgical. The primary endpoint will be tested using Cox proportional hazards regression. The primary endpoint will be tested for superiority after the secondary endpoints have been analyzed. The primary endpoint analyses will also be performed on the Per Protocol (PP) population.

Analysis of Secondary Endpoint

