4 INVESTIGATIONAL PLAN

4.1 Overall Study Design and Plan

This study is a prospective, non-inferiority, multicenter, randomized, open-label trial to compare HemoStyp with Surgicel in the management of bleeding during surgeries.

Approximately 234 subjects will be randomized in a 1:1 ratio to either HemoStyp or Surgicel. Treatment randomization will be stratified by study centers and generated prior to study initiation. It is anticipated that approximately 710 subjects will be screened to enroll approximately 236 subjects with an anticipated drop-out rate of approximately 10%.

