8.7 Assessment of Target Bleeding Sites

During the surgical procedure on Day 1, appropriate target bleed sites will be identified, characterized, and recorded on the eCRF.

A specific bleeding area/site will be defined as the target bleeding site (TBS) when it is determined by the investigator that control of bleeding by conventional surgical techniques (including suture, ligature, and cautery) is ineffective or impractical and will require an adjunct treatment to achieve hemostasis. When the TBS is identified, the investigator will rate the intensity of the bleeding at the TBS according to the validated bleeding scale (Lewis 2017) shown in the table below. Only subjects with a TBS qualitative description of mild or moderate severity will be randomized.

The surgical raters used for intraoperative recruitment of patients will be trained on a video library of different bleeding rates. These videos will be verified with gravimetric measurements of blood loss. Inter- and Intra-rater reliability will be assessed prior to protocol participation. Inter- and Intra-rater concordance should exceed 90% for a bleeding grade of “0” or hemostasis and a bleeding grade of “3” or severe bleeding.

Validated Bleeding Severity Scale				
Grade	Visual presentation	Anatomic appearance	Qualitative description	Visually estimated rate of blood loss (mL/min)
0	No bleeding	No bleeding	No bleeding	≤1.0
1	Ooze or intermittent flow	Capillary-like bleeding	Mild	>1.0-5.0
2	Continuous flow	Venule and arteriolar-like bleeding	Moderate	>5.0-10.0
3	Controllable spurting and/or overwhelming flow	Noncentral venous- and arterial-like bleeding	Severe	>10.0-50.0
4	Unidentified or inaccessible spurting or gush	Central arterial- or venous-like bleeding	Life threatening*	>50.0

* Systemic resuscitation is required (e.g., volume expanders, vasopressors, blood products, etc.).
The scale is designed and validated for use in clinical studies to generate labeling claims. The scale is a Likert-type scale, in which the user assigns a grade based on the overall agreement of the items listed.
Source: Lewis 2017

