11.2.5 Efficacy Analyses

Primary Endpoint

The time to hemostasis will be measured from start of study treatment to the achievement of hemostasis at the target bleeding site (TBS), or to the end of the 10-minute observation period. The time to hemostasis will be considered as censored at the end of the 10-minute observation period. Time to hemostasis will be quantified in minutes according to its nominal time point. When re-bleeding occurs, and the cessation of bleeding is again achieved at a later time point, the effective time to hemostasis will be the latter time point. The time to hemostasis will be the time from start of study treatment to that last effective hemostatic time point.

Secondary Endpoints

- Percentage of subjects achieving hemostasis at the target bleeding site at 2 minutes and at 5 minutes following the start of study treatment;
- Percentage of subjects with intraoperative hemostasis at the target bleeding site;
- Percentage of subjects with intraoperative re-bleeding from the target bleeding site post hemostasis;
- Postoperative re-bleeding from the target bleeding site requiring surgical re-exploration up to 30 days after surgery.

Analysis of the Primary Endpoint

The primary endpoint analyses will be based on ITT population. The primary analysis is the test of non-inferiority of HemoStyp compared with Surgicel. Cox proportional hazards regression or log-rank test will be used for the analysis of non-inferiority.

The null hypothesis for the testing of the primary endpoint is described below:

H0: HemoStyp is inferior or worse than Surgicel by more than 1 minute for median survival (HR<0.8);

H1: HemoStyp is inferior to Surgicel by less than 1 minute for median survival (HemoStyp is not inferior to Surgicel) ($HR > 0.8$);

If the lower bound 95% confidence interval of $HR > 0.8$, we conclude that HemoStyp is not inferior to Surgicel.

The primary endpoint analyses will also be performed on the PP population.

Analyses of Secondary Endpoints

A two-sided z-test with pooled variance will be used to test the difference for each secondary endpoint. The 95% confidence intervals (CIs) for each secondary endpoint in each group (HemoStyp or Surgicel) will be provided.

Secondary endpoints will be assessed at significant level of 0.05 in the order listed below after achievement of a significant result for the primary endpoint:

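### The primary Cox or log-rank analysis names neither the randomisation stratum (centre) nor the pre-allocation bleeding grade; if these are prognostic, superiority power is lost

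*Combined protocol and SAP*

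**What the plan says.** On allocation, section 4.1 states: "Treatment randomization will be stratified by study centers and generated prior to study initiation". Section 4.1.1 adds sealed envelopes for each centre. The synopsis plans for 10 to 15 centres ("Number of Sites: 10-15 sites").

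On bleeding grade, section 8.7 states: "When the TBS is identified, the investigator will rate the intensity of the bleeding at the TBS according to the validated bleeding scale". It continues: "Only subjects with a TBS qualitative description of mild or moderate severity will be randomized". Grade 1 or 2 is therefore known for every subject before allocation.

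On the analysis, section 11.2.5 states: "The primary analysis is the test of non-inferiority of HemoStyp compared with Surgicel", and then: "Cox proportional hazards regression or log-rank test will be used for the analysis of non-inferiority". The synopsis names Cox regression only. Neither place names a stratum, a covariate or a method for ties. Bleeding grade and type of surgery appear in the analysis only as subgroup factors, and centre does not appear at all.

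The synopsis also plans a superiority claim: "The primary endpoint will be tested for superiority after the secondary endpoints have been analyzed". Section 11.2.5 does not mention that test.

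**The concern.** The design balances treatment within centre, but the analysis as written does not use that balance. Surgeon and case mix differ between centres, and the two eligible grades are defined in section 8.7 by different estimated rates of blood loss (above 1 to 5 mL/min against above 5 to 10 mL/min). Either factor could plausibly predict time to hemostasis.

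If so, two things follow for an unadjusted Cox model. First, leaving out a prognostic factor attenuates the hazard ratio toward 1, even in a perfectly randomised trial. Second, the model-based standard error still carries between-centre variation that the stratified allocation has removed from the treatment comparison, so it is too large. With a true hazard ratio above 1, both work against the superiority test. They also affect the interval on which the non-inferiority decision rests.

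**Working it through.** **1. The plan's own figures.** Inputs from section 11.1: 212 subjects, 80% power, 0.05, hazard ratio (HR) 1.33, non-inferiority ratio 0.75, event proportions 0.90 and 0.92 (mean 0.91).

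Schoenfeld events = (z_alpha + z_beta)² / (0.25 × [ln(HR/margin)]²). With two-sided 0.05: 7.85 / (0.25 × 0.573²) = 95.7, or 96 events. Then 95.7/0.91 = 105.1, about 106 subjects in total. That equals the plan's per-arm figure, so 212 is not reproduced. This is a separate matter; 212 is kept below as the stated analysed number.

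With 212 subjects there are 212 × 0.91 = 193 events. Power = Φ(√(events/4) × ln(HR/bound) − 1.96), and √(192.9/4) = 6.945.

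- Non-inferiority, bound 0.8 (the decision rule in section 11.2.5): 6.945 × 0.508 = 3.53; Φ(1.57) = 94.2%.
- Superiority, bound 1: 6.945 × 0.285 = 1.98; Φ(0.02) = 50.8%.
- Superiority at 80% power: 7.85 / (0.25 × 0.285²) gives 387 events, or 387/0.91 = about 426 subjects.

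**2. Simulation set-up.** From the documents: 212 subjects, 1:1 within centre, Surgicel median 4 minutes, HR 1.33, inspection every 30 seconds, censoring at 10 minutes. Assumed: 12 centres, exponential times, grades split 50/50, and the prognostic strengths. Strength is the SD of centre effects on the log hazard and the HR for grade. There were 2,000 replicates with Efron ties. Unadjusted Cox was compared with Cox stratified by centre with grade as a covariate.

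**3. Results at a conditional HR of 1.33** (unadjusted v adjusted):

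| Centre SD; grade HR | Mean HR | Superiority power | Non-inferiority power, bound 0.8 |
|---|---|---|---|
| 0; 1.0 (none) | 1.34 v 1.34 | 49.5% v 46.6% | 92.8% v 90.5% |
| 0.3; 0.7 (weak) | 1.30 v 1.33 | 41.2% v 42.9% | 91.8% v 91.2% |
| 0.5; 0.5 (moderate) | 1.27 v 1.33 | 32.9% v 40.8% | 87.6% v 90.2% |
| 0.7; 0.35 (strong) | 1.23 v 1.33 | 23.9% v 39.7% | 82.4% v 89.2% |

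The superiority change is −2.9, +1.7, +7.9 and +15.8 points. Monte Carlo error for each superiority power is at most √(0.25/2000) = 1.1 points. The no-effect row agrees with step 1, allowing for fewer events: 86% of simulated subjects reach hemostasis, because an exponential median of 4 minutes gives only 1 − 2^(−10/4) = 82% by 10 minutes.

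**4. Which element does the work** (1,500 replicates; superiority power unadjusted, grade only, centre strata only):

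- No effect: 49.5%, 49.5%, 46.3%.
- Weak: 40.3%, 42.2%, 40.6%.
- Moderate: 32.0%, 35.8%, 37.1%.

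The grade covariate costs nothing when it is not prognostic. The loss in the no-effect row comes from stratifying on centres of about 212/12 = 18 subjects.

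**5. True HR exactly at the 0.8 bound** (none, weak, moderate, strong). The unadjusted HR averages 0.80, 0.81, 0.83 and 0.85; the adjusted HR stays at 0.80. Trials passing, unadjusted v adjusted: 2.2% v 2.4%, 2.2% v 2.5%, 2.6% v 2.5%, 3.3% v 2.7%. Monte Carlo error at 2.5% is √(0.025 × 0.975/2000) = 0.35 points.

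**6. Standard error and sensitivity to N.** Two further simulations used 236 subjects and the moderate strengths. The mean reported unadjusted standard error was 0.150 against an actual spread of 0.141 (ratio 1.06) in one, and 0.144 against 0.131 (1.10) in the other. In the second, reported and actual agreed at 0.151 for the adjusted model. Superiority power was 35% v 48% and 36% v 46%.

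**The case against.** **The plan is silent; it does not reject adjustment.** A reader might infer that the sponsor chose an unadjusted model. The documents do not support that: section 11 calls itself a brief overview and defers detail to a later SAP. This stands, and the point is only that neither factor is named. Deferral does not settle it, however. The SAP is required only before database lock, the trial is open-label, and an interim analysis follows 118 subjects. A choice between Cox and log-rank, adjusted or not, could then be made with results in view.

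**The size is assumed.** This stands in full. The documents give no figure for how strongly centre or grade predicts the outcome. With weak effects the gain is about 2 points, close to simulation error, and with none adjustment costs power. Section 8.7 sets a rater-concordance target only for grades 0 and 3, so misclassification between grades 1 and 2 would shrink any gain. Block size is not stated either.

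**The superiority test is peripheral.** It comes after the secondary endpoints, and the trial's decision is non-inferiority, where power moves little except under strong effects. Superiority power is only about 51% before any attenuation, so sample size is the larger limit and adjustment would not rescue that test. This limits the importance of the point but does not remove it.

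**The unadjusted HR is a legitimate marginal quantity.** That is correct. It is a reason to state which HR the margin refers to.

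**Conclusion.** The point holds as a cheap improvement to the primary analysis. The design stratifies by centre and records grade before allocation, and the analysis names neither. If they are prognostic, the unadjusted HR is attenuated (from 1.33 to between 1.30 and 1.23 in the scenarios tried) and, under the moderate strengths, its standard error is about 6% to 10% too large. Adjustment changes superiority power by about −3 to +16 points and non-inferiority power at the 0.8 bound by about −2 to +7 points. All of these rest on assumed prognostic strengths, 12 centres and exponential times.

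A reader might also infer that attenuation makes a device at the non-inferiority limit too likely to pass. The estimate does move that way, but the oversized standard error largely offsets it. Unadjusted pass rates stay near 2.5%. The highest in the main simulation, 3.3% v 2.7% under the strongest assumption, is too small a difference against Monte Carlo error to claim inflation. The runs with 236 subjects (3.4% v 3.0% and 2.5% v 1.8%) show no clear excess either.

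**What to change.** In the synopsis and section 11.2.5, name one primary model: Cox regression stratified by study centre, with bleeding severity grade (1 v 2, as rated before allocation) as a covariate. Fix in advance a rule for pooling very small centres and a tie method suited to the 30-second inspection grid. Take both the non-inferiority confidence interval and the superiority test from this model, and state that the margin applies to this conditional HR. Keep the unadjusted Cox model as a sensitivity analysis. Type of surgery may be added as a covariate, but it was not simulated and no gain from it has been shown.

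The change is to wording only, since centre and grade are already known for every randomised subject. The statistical cost is about 1 to 3 points of power if neither factor is prognostic.

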4.1.1 Randomization

Randomization will be assigned using sealed envelopes for each arm and each study center.

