7.2 Study Treatment Day 0 (Visit 2 – Surgery)

On Day 1, eligible subjects will report to the hospital/surgical site at the scheduled time. Prior to surgery, the following procedures will be performed:

- Review of inclusion and exclusion criteria; and
- Review and record any changes to concomitant medications.

Other procedures will be performed in accordance with the pre-surgical and surgical site standards.

During the surgical procedure, subjects with appropriate target bleed sites (TBS) as determined using the validated bleeding severity scale (see [Section 8.6](#)) will be randomized to their assigned treatment (HemoStyp or Surgicel).

Each treatment will be applied in accordance with technical instructions provided in the investigator manual. Upon application of the study treatment at target bleeding site, a stopwatch will be started with inspection for bleeding occurring every 30 seconds for 10 minutes. In addition, the investigator will inspect the target bleeding site for 5 minutes after hemostasis is presumed to be achieved to ensure rebleeding does not occur.

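### The sealed-envelope sentence, read literally, sorts envelopes by arm, and nothing else in the plan secures concealment in this open-label trial with intraoperative eligibility

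*Combined protocol and SAP*

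**What the plan says.** Section 4.1.1 gives the allocation mechanism in full: "Randomization will be assigned using sealed envelopes for each arm and each study center". Section 4.1 adds the ratio and the source of the sequence: "Approximately 234 subjects will be randomized in a 1:1 ratio to either HemoStyp or Surgicel", and "Treatment randomization will be stratified by study centers and generated prior to study initiation". It also states that the trial is open-label.

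Randomization takes place during the operation (Section 7.2). Under Section 8.7 the investigator decides that a site needs an adjunct and then grades it: "When the TBS is identified, the investigator will rate the intensity of the bleeding at the TBS according to the validated bleeding scale". Entry depends on that grade: "Only subjects with a TBS qualitative description of mild or moderate severity will be randomized".

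The plan does not say:
- whether envelopes are opaque, sequentially numbered or identical in appearance;
- whether the two arms are mixed in one series;
- who prepares, holds or opens the envelopes;
- that the grade must be written down before opening, or that opening is logged;
- what block sizes are used.

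Interactive voice and web response systems appear only in the abbreviation list. The master randomization list appears only in Section 14.5, as a record to keep where applicable.

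**The concern.** Concealment means that the person deciding on entry cannot know the next assignment. If envelopes are held as one set per arm at each centre, the set reveals the treatment and sealing achieves nothing.

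This trial is exposed to that weakness. The person who selects the site and grades the bleeding does so by eye, minutes before allocation, and will see which product is applied. A surgeon who knew the next product could, without any intent to mislead, accept an easier bleed for one arm or pass over a harder one for the other. Bleeding intensity plausibly predicts time to hemostasis, so the primary hazard ratio would absorb the difference. In a non-inferiority trial, a shift towards HemoStyp raises the chance of a false claim. A shift towards Surgicel costs power.

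**Working it through.** The plan states no figure on this point, so there is none to reproduce. The check compares the relevant sections and then sizes the risk under stated assumptions.

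**1. What the sections support together**

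| Question | Where | Answer |
|---|---|---|
| How are envelopes organised? | 4.1.1 | By arm and by centre |
| How is the sequence made? | 4.1 | In advance, stratified by centre, 1:1 |
| Is treatment masked? | 4.1 | No |
| Who controls entry? | 7.2, 8.7 | The investigator, by visual grade, during surgery |
| Is grading checked? | 8.7 | Raters are trained on video; concordance above 90% is required for grades 0 and 3 only |
| Does the primary model adjust for grade? | 11.2.5 | None stated; grade appears only as a subgroup |

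The concordance requirement covers the grades bordering the eligible range. It sets no threshold for mild against moderate, which is the distinction that separates easier from harder bleeds among randomized subjects.

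**2. Effect on the non-inferiority error (assumed bias)**

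Inputs:
- Section 11.1: 212 subjects, with event proportions 0.90 and 0.92 (mean 0.91).
- Events: D = 212 × 0.91 = 192.9, about 193.
- Section 11.2.5: the decision uses the lower 95% confidence limit, taken here as one-sided 0.025, so z = 1.96.
- Assumption: the true hazard ratio equals the margin, and selection multiplies it by b in favour of HemoStyp.

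Formula: error = Φ(√(D/4) × ln b − 1.96), with √(192.9/4) = 6.945.

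| b | 6.945 × ln b | Minus 1.96 | Error |
|---|---|---|---|
| 1.00 | 0 | −1.960 | 2.5% |
| 1.05 | 0.339 | −1.621 | 5.3% |
| 1.10 | 0.662 | −1.298 | 9.7% |
| 1.15 | 0.971 | −0.989 | 16.1% |

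The margin cancels, so the result is the same for 0.75 (Section 11.1) and 0.8 (Section 11.2.5).

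**3. What would produce b near 1.15 (assumed)**

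Suppose moderate bleeds make up 40% of the HemoStyp arm and 60% of the Surgicel arm, and reach hemostasis at half the rate of mild bleeds. Then b ≈ exp(0.20 × ln 2) = exp(0.139) = 1.149, and a true hazard ratio of 0.80 would appear as about 0.80 × 1.149 = 0.92. Simulation with 30-second inspections and censoring at 10 minutes gave an unadjusted value of about 0.92 to 0.94. A Cox model stratified by grade returned about 0.80. A smaller imbalance gives a smaller b.

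**4. Why block size matters as well**

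With 10 to 15 sites, a centre randomizes on average 234/15 = 15.6 to 234/10 = 23.4 subjects. In an open-label trial with known fixed blocks of 4, the best guess is right with probability 1/2, 2/3, 2/3 and 1 at the four positions, a mean of 2.833/4 = 71%. One third of assignments are certain. A mixed series with fixed, known blocks would therefore still leak.

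**The case against.** The strongest reply is that the sentence is loose drafting. It does not say that envelopes are labelled, stored or drawn by arm. If they were, sealing would be pointless and someone would be choosing the treatment, which contradicts the pre-generated, centre-stratified sequence in Section 4.1. On this view the sentence means only that envelopes carrying both assignments are supplied to each centre. That is plausible, and a reader who infers that the arm is visible to the surgeon goes further than the text allows. However, 10 to 15 sites have to act on this sentence, and no other section states the safer arrangement.

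A reader might also infer that no later analysis could repair the damage. That is too strong. Grade is rated before randomization, and in the illustration stratifying by it removed essentially all of the bias. It would not remove selection within a grade, or misgrading influenced by knowledge of the arm. The primary analysis as written names no such adjustment.

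Nor is concealment the only protection. Section 8.7 requires rater training on videos verified by measured blood loss, and reliability is assessed beforehand. Sections 7.2 and 8.7 already place site identification and grading before randomization. These safeguards stand, but they do not hide the next assignment, and the plan has no explicit rule that the grade be recorded before the envelope is opened.

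Finally, the bias factors are assumed. That is correct, and they show sensitivity only.

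**Conclusion.** The point holds as a defect in the stated allocation method. Taken literally, Section 4.1.1 defeats concealment. Taken charitably, it leaves concealment undescribed beyond the word sealed. Under either reading, an open-label trial in which the investigator grades the bleed just before allocation needs more.

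The documents do not show that the arm will in fact be visible, or that any bias has a particular size. If the true hazard ratio is at the margin, about 193 events occur and selection favours HemoStyp by a factor of 1.05 to 1.15, the one-sided 0.025 error becomes about 5% to 16%. If envelopes are in practice mixed, opaque and opened in order, and the next assignment cannot be predicted, this route to bias closes. The change should be made before sites are supplied, because grade adjustment is only a partial remedy.

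**What to change.** Replace the sentence in Section 4.1.1 with:

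*One series per centre of sequentially numbered, opaque, externally identical sealed envelopes, both arms mixed in the pre-generated order with randomly varying block sizes not disclosed to sites; each is opened in sequence only after the target site and its Lewis grade are recorded, and the time of opening is logged.*

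The cost is envelope preparation and a short log at each centre. No web system or added staff is needed, and sample size and clinical procedures do not change. If one mixed series per centre was always intended, the edit records that intention and adds the missing safeguards.
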